# 12. STATISTICAL ANALYSIS

- *Describe how your data will be used to test the hypotheses.*
- State clearly what variables will be tested and what statistical tests will be used.
- *Include sample size calculations.*
- If this is a pilot study, state which variables will be examined for hypothesis generation in later studies.

This is a randomized controlled trial in women to compare two methods of voiding after undergoing surgical repair for pelvic organ prolapse [POP]. The two methods are: the traditional retrograde bladder filling method and the force of stream trial (FAST). The study is designed as a non-inferiority trial to demonstrate that among patients who are discharged without a urinary catheter (because they passed the post-op voiding trial), the rate of catheterization within the six-week post-operative period in subjects undergoing the FAST voiding trial is not worse than in subjects undergoing the traditional retrograde voiding trial.

# **Specific Aims:**

- The primary objective of the study is to compare Traditional voiding trial to FAST voiding trial with respect to the rate of catheterization within the six-week postoperative period in patients undergoing surgical repair of POP, among those discharged without a urinary catheter.
- 2. Secondary objectives include:
  - a. To compare the two voiding methods with respect to the proportion of patients discharged with a catheter (these are the subjects who fail the voiding trial)

Version Date: 2/26/16 Page 9 of 25

- b. To compare the two voiding methods with respect to the incidence of any UTI within the six-week post-operative period
- c. To compare the two voiding methods with respect to the rate of emergency room visits or unexpected visits to the clinic within the six-week post-operative period for voiding dysfunction or suspected infection (this includes patients who were discharged with or without a urinary catheter)
- d. To compare the two voiding methods with respect to the time-to-catheterization post-discharge.
- e. To compare the two voiding methods with respect to patient satisfaction with post-operative bladder function using the American Urological Association Symptom Score and the Urinary Distress Inventory.

#### **Primary Outcome:**

The primary outcome variable of interest is the rate of catheterization within the six-week post-operative period following surgical repair of POP, among those discharged without a urinary catheter. (The primary outcome will be the overall rate (regardless of stratification) but catheterization rates by surgery type will also be examined.)

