#### **Randomization:**

Subjects will be randomized in a 1-1 ratio to either the Traditional voiding trial or the FAST voiding trial. Randomization will be stratified by site (North Shore or Long Island Jewish), and within each site, by surgical type (apical prolapse surgery without sling or apical prolapse surgery with sling).

The Biostatistics Unit at the Feinstein Institute for Medical Research [BU-FIMR] will develop a randomization plan using the Biostatistics Randomization Management System [BRMS]. BRMS is a secure, HIPAA-compliant, web-based application that allows investigators to randomize subjects into randomized clinical trials (RCTs) using a personal computer with internet access. Randomization notifications are automatically sent to the PI and other authorized personnel. BRMS maintains compliance in RCTs. Details of the randomization procedure will be further developed upon approval of the protocol.

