## **Statistical Methods:**

1. For the primary objective:

The test for non-inferiority will be carried out using a two-tailed 95% confidence interval for the difference in the rate of catheterization between the two voiding methods, within the six-week post-operative period,  $\delta$  ( $\delta$ =rate of catheterization in the FAST voiding trial – rate of catheterization in the Traditional voiding trial). This difference,  $\delta$ , is the margin of non-inferiority and will be set at 10%. If the upper confidence limit for the difference is  $<\delta$  ( $\ge\delta$ ) then we will conclude that the FAST voiding trial is non-inferior (inferior) to the Traditional voiding trial.

The test for non-inferiority will be performed only for the primary outcome variable of interest, i.e., catheterization within the six-week post-operative period among subjects who were discharged without needing a urinary catheter.

The test for non-inferiority will also be performed according to surgery type (the stratification variable).

- For the secondary objectives:
  - a. The chi-square test or Fisher's exact test, as appropriate, will be used to compare the two voiding methods with respect to the proportion of subjects who are sent home with a catheter due to failure of their voiding trial, post-surgery.
  - b. The chi-square test or Fisher's exact test, as appropriate, will be used to compare the two voiding methods with respect to the proportion of subjects who present with any UTI within the six-week post-operative period. If feasible, the incidence of UTIs will be compared between the two voiding methods using the Incidence Density Ratio Method, or if feasible, Poisson regression methods.
  - c. The chi-square test or Fisher's exact test, as appropriate, will be used to compare the two voiding methods with respect to the proportion of subjects who present to the emergency room or the urogynecology clinic (unexpectedly) due to voiding dysfunction or suspected infection, within the six-week post-operative period. If feasible, the incidence of ER visits or unexpected clinic visits will be compared between the two voiding methods using the Incidence Density Ratio Method, or if feasible, Poisson regression methods.

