  - d. The Kaplan-Meier product limit method will be used to estimate time-to-catheterization post-discharge and the two groups (Traditional Retrograde vs. FAST) will be compared using the log-rank test. Median time-to-catheterization will be estimated along with their corresponding 95% confidence intervals. The feasibility of this analysis will depend on the observed catheterization rates.
  - e. A mixed models approach to repeated measures analysis of variance (MM-RMANOVA) will be carried out, separately, for each of the two measures of patient satisfaction with post-operative bladder function (AUASS and UDI-6). Each model will examine if the patterns of change in satisfaction scores across

Version Date: 2/26/16 Page 11 of 25

time (baseline, 2 weeks post-op and 6 weeks post-op) differ between the two voiding methods. The models will include voiding group (Traditional/FAST), time (baseline, 2 weeks post-op and 6 weeks post-op) and a group-by-time interaction term. Data transformations may be employed if standard model assumptions are not met. If no suitable transformations are found, then appropriate non-parametric methods may be used instead.

A secondary analysis using logistic regression, will be carried out for each of the aims 2a, 2b and 2c, including explanatory variables such as age, site, and surgery type (sling vs. no sling).

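### Randomisation is stratified by site and sling, but the primary difference is crude, in a subset where balance on those strata is no longer guaranteed

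*Combined protocol and SAP*

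**What the plan says.** All references are to the combined protocol and SAP, section 12, unless stated.

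- Randomization: "Randomization will be stratified by site (North Shore or Long Island Jewish), and within each site, by surgical type" (with or without a sling), which makes four strata. Allocation is 1:1.
- Primary Outcome: "The primary outcome will be the overall rate (regardless of stratification"), with rates by surgery type to be looked at as well. The analysis set is restricted to women "among those discharged without a urinary catheter".
- Statistical Methods, primary objective: "The test for non-inferiority will be carried out using a two-tailed 95% confidence interval for the difference in the rate of catheterization". The upper limit is compared with 10%. No stratified or adjusted estimator is named.
- The same section adds: "The test for non-inferiority will also be performed according to surgery type (the stratification variable"). Site is not mentioned for the primary outcome.
- Statistical Methods, secondary objectives: "A secondary analysis using logistic regression, will be carried out for each of the aims 2a, 2b and 2c", with age, site and surgery type as explanatory variables. The primary aim is not in that list.

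**The concern.** A crude analysis after stratified randomisation is usually defended on the ground that the design has already balanced the strata. That balance applies to the women randomised. Here a woman enters the primary analysis only if she passes the test to which she was randomised.

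Section 11 gives the arms different pass rules. The retrograde arm depends on the volume voided. The FAST arm depends on perceived force of stream, with a second route through a bladder scan. If having a sling affects passing differently under the two rules, the arms will differ in sling mix among passers. If catheterisation is also more frequent with a sling, that mix enters the primary difference.

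The trial has little slack. It expects 59 × 0.05 ≈ 3 events per arm, and one event is 1/59 = 1.7 points.

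**Working it through.** **Inputs from section 12 (Sample Size Considerations, Statistical Methods):** rate 5% in both arms, margin 10 points, 80% power, 59 passers per arm, 77 evaluable per arm, about 30% failing in each arm, two-tailed 95% interval. **Not given, so assumed:** sling share s, rates by sling, and pass rates by arm and sling.

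1. **The plan's own figure.** n = (z₁₋α + z₀.₈₀)² × 2 × 0.05 × 0.95 / 0.10². With one-sided α = 0.05 this is (1.645 + 0.842)² × 9.5 = 58.7, so 59, as stated. The formula has no term for strata. (With one-sided 0.025, matching the two-tailed 95% interval, it gives 75. That mismatch is a separate matter. Together with 77 × 0.7 ≈ 54 passers per arm, it explains why the power figures below start near 68%.)

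2. **Room below the margin.** At 5% in each arm and 59 per arm, the half-width is 1.96 × √(2 × 0.0475/59) = 7.9 points, which leaves 10 − 7.9 = 2.1 points.

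3. **When the sling mix differs.** If π₁ and π₀ are an arm's pass rates with and without a sling, the sling share among its passers is sπ₁ / [sπ₁ + (1 − s)π₀]. This depends on the arm only through π₁/π₀. With no true difference within strata, the crude difference equals (FAST share − Traditional share) × (sling rate − no-sling rate).
   - *Same pass rate everywhere (70%).* Expected shift is 0. The sling share still differs between arms by chance, with SD about 5 points.
   - *About 30% failing in each arm overall.* Take s = 0.3, FAST 70%/70% and Traditional 60%/75% (sling/no sling). Overall pass rates are 70% and 0.3 × 60% + 0.7 × 75% = 70.5%. Sling shares are 0.300 and 0.18/0.705 = 0.255. With rates of 11.36% and 2.27% (a fivefold ratio averaging 5%), the shift is 0.0447 × 9.09 = +0.41 points. With a twofold ratio it is +0.17.
   - *Stronger interaction.* FAST 90%/80%, Traditional 60%/80%, s = 0.3: shares are 0.27/0.83 = 0.325 and 0.18/0.74 = 0.243. The shift is 0.0821 × 9.09 = +0.75 points. Exchanging the arms' pass rates gives −0.75, which favours FAST.
   - The largest case tried (FAST 95%/95%, Traditional 50%/80%, fivefold ratio, s = 0.3) gives +0.81.

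4. **Power, by simulation** (77 per arm balanced on sling, two-sided 95% limit against 10%, no true difference; crude Wald against Mantel-Haenszel with Sato variance, stratified by sling).
   - Equal pass rates: crude 68–69%, stratified 68–70%.
   - FAST 90%/80%, Traditional 60%/80%, s = 0.3 or 0.5, sling ratio 2 to 5: crude 68–72% with a shift of +0.3 to +0.75; stratified 74–76% with a shift of about 0.
   - A further simulation with 40% sling and shifts of about ±0.8 points: crude power 66% or 77% according to direction, stratified 74% or 72%.
   - At a true difference of 10 points with equal pass rates, both methods concluded non-inferiority in about 3.7–3.9% of runs (nominal 2.5%). Stratifying neither causes nor cures that.

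5. **Precision alone.** The ratio of within-stratum to pooled variance, for equal-sized strata, is 0.981 at rates of 2% and 8%, 0.972 at 2% and 10%, and 0.946 at 2% and 15%. The 7.9-point half-width shrinks by only about 0.08, 0.11 and 0.22 points.

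6. **Choice of interval.** In a simulation with four strata, 60% without a sling and 70% passing everywhere, the chance of concluding non-inferiority was:
   - Miettinen-Nurminen: 51.2% crude and 50.2% stratified (5% rate in all strata); 49.8% and 48.1% (2% and 10%).
   - Newcombe: 53% crude and 37% for one stratified version (5% rate in all strata).
   - At least one stratum had no events in either arm in 71–82% of runs.

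7. **Tests by surgery type.** The smaller surgery-type stratum has at most about 29 passers per arm. At a 5% rate the half-width is at least 1.96 × √(2 × 0.0475/29) = 11.2 points, which exceeds the margin even at zero observed difference.

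**The case against.** The crude overall rate is a declared choice, and sling is not ignored: the plan reports rates and repeats the test by surgery type. The plan also assumes about 30% failure in both arms. If that held in every stratum there would be no bias to remove. Every non-zero shift above rests on pass rates that no document gives, and even the largest is under a tenth of the margin. The precision gain is negligible, and with about 3 events per arm some stratified intervals do worse than the crude one.

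Most of this stands. It rules out several stronger readings that a reader might reach:

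- *That the crude comparison is known to be biased.* It is not; the shift is conditional on unequal pass rates.
- *That the strata play no part in the primary outcome.* Surgery type does; site does not.
- *That the plan regards the two factors as prognostic.* It gives no reason for stratifying.
- *That stratifying would materially narrow the interval.* It would not.

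Three things do not stand. The tests by surgery type give two separate and imprecise answers, not one adjusted answer. Equal overall failure does not imply equal failure by sling, as the 70% and 70.5% example shows. And the poor result for one stratified Newcombe interval does not carry over to the Mantel-Haenszel difference with Sato variance, which lost essentially nothing with equal pass rates.

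**Conclusion.** The point holds as a modest, nearly free improvement. The primary estimate departs from the randomisation scheme in a set where that scheme's balance can be lost. With equal pass rates across arms and strata, expected bias is zero and power is essentially the same either way. With pass rates that differ by arm and sling, the shift in the cases tried was about 0.2 to 0.8 points in either direction, and a stratified estimate removes it. A shift of 0.8 is small against 10 points, but it is 0.8/2.1 = 38% of the room left at the planned rates and 59 per arm. A shift favouring FAST would make non-inferiority easier to conclude.

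These sizes depend on an assumed sling share of 30–50% and catheterisation two to five times as frequent with a sling. A reader might also infer that stratifying makes the passers comparable. It restores comparability on site and sling only; selection on any other cause of passing remains.

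**What to change.** Amend Primary Outcome and Statistical Methods in section 12, before outcome data are seen by arm, to state:

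- The primary estimate is the Mantel-Haenszel risk difference (FAST minus Traditional) with Sato variance. The upper limit of its two-sided 95% interval is compared with 10%.
- Strata are sling by site, as recorded at randomisation, provided every cell has passers in both arms; otherwise collapse over site and stratify by sling alone. Strata with passers but no events are kept.
- The crude difference is reported as supportive, and the results by surgery type as descriptive of each stratum.
- A stratified Newcombe interval is not to be substituted as if equivalent, because it can lose substantial power with about 3 events per arm.
- Numbers passing are tabulated by arm, sling and site, so that any imbalance is visible.

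The cost is a paragraph of SAP text and slightly more analysis work. The strata are already recorded, so no new data are needed, and no change in sample size follows from this point. Little precision is gained.

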#### **Secondary Outcomes**

- 1. Proportion of patients discharged with a catheter (this is essentially the proportion of patients who failed the voiding trial)
- 2. Proportion of patients who reported *any* UTI within the six-week post-operative period. The number of UTIs reported by each patient during that period will also be recorded.
- Proportion of patients with emergency room visits or unexpected visits to the Urogynecology clinic for voiding dysfunction or suspected infection, within the sixweek post-operative period. The number of ER visits or unexpected clinic visits will also be recorded.
- 4. Time-to-catheterization post-discharge: This is the number of days from discharge to catheterization (within the 6-week period post-surgery). Subjects who are not catheterized by the end of the follow-up period will be considered 'censored'.
- 5. Patient satisfaction with postoperative bladder function (measured at baseline, 2-weeks post-op and 6 weeks post-op) using:
  - c. American Urological Association Symptom Score (AUASS)
  - d. Urinary Distress Inventory (UDI-6)

#### **Randomization:**

Subjects will be randomized in a 1-1 ratio to either the Traditional voiding trial or the FAST voiding trial. Randomization will be stratified by site (North Shore or Long Island Jewish), and within each site, by surgical type (apical prolapse surgery without sling or apical prolapse surgery with sling).

The Biostatistics Unit at the Feinstein Institute for Medical Research [BU-FIMR] will develop a randomization plan using the Biostatistics Randomization Management System [BRMS]. BRMS is a secure, HIPAA-compliant, web-based application that allows investigators to randomize subjects into randomized clinical trials (RCTs) using a personal computer with internet access. Randomization notifications are automatically sent to the PI and other authorized personnel. BRMS maintains compliance in RCTs. Details of the randomization procedure will be further developed upon approval of the protocol.

## **Data Management**

REDCap (Research Electronic Data Capture), a secure, web-based application, will be used to store data from the trial.

# **Intention-to-Treat (ITT)**

Version Date: 2/26/16 Page 10 of 25

All subjects will be analyzed according to the intention-to-treat [ITT] principle. A patient will be considered evaluable and will be included in the intention-to-treat analysis if the patient was randomized to either voiding trial group and able to undergo the voiding trial after surgery. Analyses that take into account the actual voiding trial received will be carried out as a secondary analysis (per protocol [PP] analysis).

#### Interim Analysis and Early Stopping

No interim analysis is planned for this study.

## **Statistical Methods:**

1. For the primary objective:

The test for non-inferiority will be carried out using a two-tailed 95% confidence interval for the difference in the rate of catheterization between the two voiding methods, within the six-week post-operative period,  $\delta$  ( $\delta$ =rate of catheterization in the FAST voiding trial – rate of catheterization in the Traditional voiding trial). This difference,  $\delta$ , is the margin of non-inferiority and will be set at 10%. If the upper confidence limit for the difference is  $<\delta$  ( $\ge\delta$ ) then we will conclude that the FAST voiding trial is non-inferior (inferior) to the Traditional voiding trial.

The test for non-inferiority will be performed only for the primary outcome variable of interest, i.e., catheterization within the six-week post-operative period among subjects who were discharged without needing a urinary catheter.

The test for non-inferiority will also be performed according to surgery type (the stratification variable).

- For the secondary objectives:
  - a. The chi-square test or Fisher's exact test, as appropriate, will be used to compare the two voiding methods with respect to the proportion of subjects who are sent home with a catheter due to failure of their voiding trial, post-surgery.
  - b. The chi-square test or Fisher's exact test, as appropriate, will be used to compare the two voiding methods with respect to the proportion of subjects who present with any UTI within the six-week post-operative period. If feasible, the incidence of UTIs will be compared between the two voiding methods using the Incidence Density Ratio Method, or if feasible, Poisson regression methods.
  - c. The chi-square test or Fisher's exact test, as appropriate, will be used to compare the two voiding methods with respect to the proportion of subjects who present to the emergency room or the urogynecology clinic (unexpectedly) due to voiding dysfunction or suspected infection, within the six-week post-operative period. If feasible, the incidence of ER visits or unexpected clinic visits will be compared between the two voiding methods using the Incidence Density Ratio Method, or if feasible, Poisson regression methods.
  - d. The Kaplan-Meier product limit method will be used to estimate time-to-catheterization post-discharge and the two groups (Traditional Retrograde vs. FAST) will be compared using the log-rank test. Median time-to-catheterization will be estimated along with their corresponding 95% confidence intervals. The feasibility of this analysis will depend on the observed catheterization rates.
  - e. A mixed models approach to repeated measures analysis of variance (MM-RMANOVA) will be carried out, separately, for each of the two measures of patient satisfaction with post-operative bladder function (AUASS and UDI-6). Each model will examine if the patterns of change in satisfaction scores across

Version Date: 2/26/16 Page 11 of 25

time (baseline, 2 weeks post-op and 6 weeks post-op) differ between the two voiding methods. The models will include voiding group (Traditional/FAST), time (baseline, 2 weeks post-op and 6 weeks post-op) and a group-by-time interaction term. Data transformations may be employed if standard model assumptions are not met. If no suitable transformations are found, then appropriate non-parametric methods may be used instead.

A secondary analysis using logistic regression, will be carried out for each of the aims 2a, 2b and 2c, including explanatory variables such as age, site, and surgery type (sling vs. no sling).

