#### Sample Size Considerations:

The proposed sample size for this one year study is a total of 154 evaluable subjects (n=77 randomized to each voiding group). A subject will be "evaluable" if she gets randomized and is able to undergo the voiding trial. A subject who is not able to undergo the voiding trial is considered "not evaluable" and would not be included in the analysis.

The study will be designed as a non-inferiority trial, where the FAST voiding trial will be considered non-inferior to the Traditional voiding trial if the difference in the rate of catheterization between the two groups within the six-week post-operative period among patients discharged without a catheter is less than  $\delta$ =10% (i.e.  $\delta$ =10%, the margin of non-inferiority). More formally, if the rates of catheterization during the six-week post-operative period are p\_F and p\_T, respectively for the FAST and Traditional voiding methods, then the null (Ho) and alternative hypotheses (HA) are:

$$H_0$$
:  $d = p_F - p_T \ge \delta$  vs.  
 $H_A$ :  $d = p_F - p_T < \delta$ 

Based on the investigators' clinical experience, it can be reasonably assumed that among those who pass the Traditional retrograde fill voiding trial, the rate of catheterization during the six-week post-operative period is about 5%. Further assuming that the rate of catheterization among those who pass the FAST voiding trial is the same as in the traditional voiding test (i.e. 5% as well), and using a non-inferiority margin, $\delta$ , of 10%, then a sample size of 59 per group (n=118 total) will yield 80% power to determine that the FAST voiding trial is not inferior to the Traditional voiding trial (alpha=0.05).

Based on published manuscripts, about 30% of evaluable patients will fail either voiding trial, that is, approximately 30% in the traditional retrograde fill voiding trial arm will fail the test and similarly, approximately 30% in the FAST voiding trial arm will fail the test. Therefore, in order to obtain 118 subjects who pass the voiding test (59 per group), we would need to have a total of 154 subjects (118 x 1.3=154).

Randomized subjects will fall into three groups:

- 1. Subjects with a complication at surgery that would require prolonged catheterization immediately postoperative.
- 2. Subjects who fail either voiding test and are discharged home with a catheter (expected to be 25-26% based on pusblished manuscripts)

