- Subjects passing either trial of void and discharged home without a
  catheter. This is the main population of interest that we want to
  examine to identify what proportion of subjects would end up
  needing a catheter ultimately in the 6-week postoperative period.

Below is a tabulation of sample size requirements for 80% power, using various assumptions for the rates of catheterization during the six-week post-operative period in each of the two

Version Date: 2/26/16 Page 12 of 25

voiding methods, using a 2-sided alpha level of 0.05, and a non-inferiority margin,  $\delta$ , of 10%:

Traditional	FAST Voiding	Sample Size
Voiding Method	Method	Per Method (N)
0.05	0.07	109
0.05	0.06	80
0.05	0.05	59
0.05	0.04	44
0.05	0.03	33

Version Date: 2/26/16 Page 13 of 25

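### The stated 80% power holds only at one-sided 0.05, not under the two-tailed 95% interval that decides the trial, and that interval has no named method although about 3 events per arm are expected

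*Combined protocol and SAP*

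**What the plan says.** All references are to Section 12 of the combined protocol and SAP.

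- **Primary test (Statistical Methods).** "The test for non-inferiority will be carried out using a two-tailed 95% confidence interval for the difference in the rate of catheterization" between FAST and Traditional, among women discharged without a catheter. An upper limit below 10% is called non-inferior; at or above 10% it is called inferior. No construction method is given. For the secondary proportions the same section does name its tests (chi-square or Fisher's exact).
- **By surgery type.** "The test for non-inferiority will also be performed according to surgery type (the stratification variable". The Primary Outcome paragraph makes the overall rate primary.
- **Sample size.** With 5% in both arms and a 10% margin, "then a sample size of 59 per group (n=118 total) will yield 80% power". The table that follows is described as "using a 2-sided alpha level of 0.05". The plan enrols 77 evaluable women per arm and expects about 30% to fail the voiding trial; a few lines later failure is "expected to be 25-26% based on pusblished manuscripts".
- **AUASS and UDI-6.** "The models will include voiding group (Traditional/FAST), time (baseline, 2 weeks post-op and 6 weeks post-op) and a group-by-time interaction term". Site and surgery type are not in these models. They appear elsewhere as explanatory variables: "A secondary analysis using logistic regression, will be carried out for each of the aims 2a, 2b and 2c".

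**The concern.** There are three issues, in decreasing order of weight.

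1. The power statement and the decision rule use different error rates. A two-tailed 95% interval compared with a one-sided margin carries a one-sided error of 2.5%, not 5%. If 59 was derived at 5%, the trial has less power than it claims.
2. At about 3 events per arm (5% of 59 is 2.95), interval methods for a difference in proportions do not agree. If none is named, the method can be settled once the counts are known, and that choice alone can move the reported result between non-inferior and inferior.
3. The symptom-score models treat baseline as one more outcome level and let the arms differ there. This is valid, but it gives up precision that data already being collected could supply.

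**Working it through.** **Inputs from the plan:** rate 5% in each arm; margin 10%; 59 passers per group; 77 evaluable per arm; failure 30% or 25-26%; two-tailed 95% interval.

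**Reproducing 59.** Unpooled normal formula:

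n = (z_alpha + z_power)² × [p_F(1−p_F) + p_T(1−p_T)] / [margin − (p_F − p_T)]²

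- One-sided 0.05: (1.645 + 0.842)² × 0.095 / 0.01 = 58.7, so 59.
- One-sided 0.025 (what a two-tailed 95% interval delivers): (1.960 + 0.842)² × 0.095 / 0.01 = 74.6, so 75.

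| FAST rate (Traditional 5%) | Plan's table | One-sided 0.05 | One-sided 0.025 |
|---|---|---|---|
| 7% | 109 | 109 | 139 |
| 6% | 80 | 80 | 101 |
| 5% | 59 | 59 | 75 |
| 4% | 44 | 44 | 56 |
| 3% | 33 | 33 | 42 |

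All five rows match one-sided 0.05 and none matches the two-sided label.

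**Expected passers.** 77 × 0.70 = 53.9; 77 × 0.74 = 57.0. The plan inflates by 118 × 1.3 = 154, but obtaining 118 passers at 30% failure needs 118 / 0.7 = 169. So 53 to 57 per arm is the realistic range, not 59.

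**Exact power and disagreement.** All pairs of binomial counts were enumerated with 5% in both arms, and non-inferiority claimed when the upper 95% limit is below 10%.

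| Passers per arm | Power, Wald | Power, Miettinen-Nurminen | Opposite verdicts |
|---|---|---|---|
| 54 | 71% | 52% | 19.3% |
| 57 | 69% | 55% | 13.7% |
| 59 | 71% | 55% | 16.3% |
| 75 | 82% | 69% | – |

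Power does not rise smoothly with n because the counts are discrete. At 53 per arm the disagreement is 18.5%.

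**What a disagreement looks like at 59 per arm.** With 3 FAST and 2 Traditional events the difference is 1/59 = 1.69 points. The Wald standard error is √[(0.0508 × 0.9492 + 0.0339 × 0.9661)/59] = 0.0371, so the upper limit is 1.69 + 1.96 × 3.71 = 8.96%: non-inferior. Newcombe gives 10.86% and Miettinen-Nurminen 11.05%: not shown. With 4 and 4 events, Wald gives 9.07% and Miettinen-Nurminen 10.43%. With 3 and 3 events both pass.

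**Which methods disagree.** At 59 per arm: Wald against Miettinen-Nurminen 16.3%, Wald against Newcombe 12.8%, Newcombe against score 3.5%. One-sided error at the margin (15% vs 5%), nominal 2.5%: Wald 3.4%, Newcombe 2.2%, Miettinen-Nurminen 2.1%. At 13% vs 3% Wald rises to 4.5%.

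**Surgery-type tests.** With no events in either arm, the Miettinen-Nurminen upper limit is 10.02% at 35 passers per arm and 9.76% at 36. Two strata of 36 need 72 per arm, which do not fit in 59. At any sling share, at least one stratum therefore cannot meet the margin even with zero events. Wald returns an upper limit of 0% for zero events at any size.

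**Symptom scores.** Let rho be the baseline to week-6 correlation, with equal SDs and complete data. The unconstrained group-by-time contrast at week 6 has variance proportional to 2(1−rho); adjusted for baseline, or with baseline means constrained equal, it is 1−rho². The ratio is (1+rho)/2. The documents give no rho; at an assumed 0.3, 0.5 and 0.7 it is 0.65, 0.75 and 0.85. Adding site and surgery type would narrow the interval by about 0.3% to 4.5% if they explain 2% to 10% of residual variance (assumed).

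**The case against.** **The one-in-six figure is not general.** It is one pair of methods at one rate. For Wald against score at 59 per arm, disagreement is 22.3% at a common rate of 3%, 9.6% at 7%, 5.3% at 10%, and 1.2% at the null boundary of 15% vs 5%. This stands. A reader might infer that any unnamed method puts a sixth of trials in doubt; the calculations do not support that, because Newcombe and score rarely part. The issue is that nothing in the plan excludes Wald.

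**The sample-size formula is Wald-type, so Wald may be implied.** The formula does not name the analysis interval. If Wald was meant, its error at the margin exceeds the nominal 2.5%.

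**A non-inferiority test is naturally one-sided, so 59 at alpha 0.05 is defensible.** It would be if the analysis used a one-sided 5% test. The plan instead specifies a two-tailed 95% interval and labels the table two-sided.

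**The power shortfall is a sample-size matter, not an interval matter.** Largely right. A reader might blame the score method for the whole drop to 55%; Wald also reaches only 71% at 59, so naming a method does not repair the alpha mismatch.

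**Choosing Miettinen-Nurminen is preference.** Partly right. Newcombe has similar error and slightly higher power at 59 (58.6%), and would serve about as well.

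**The surgery-type tests do not drive the conclusion.** True, since the overall rate is primary. The same non-inferiority rule is nevertheless to be applied to them.

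**The symptom model is not wrong.** Correct. A reader might infer bias or an error; there is none. The gain is not entirely free either: baseline as a covariate may drop women without a baseline score, whom the planned model keeps. The site and surgery-type adjustment elsewhere is itself only a secondary analysis, so its absence here is no contradiction.

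**Conclusion.** The point holds in three parts of unequal strength.

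1. **Wrong as written.** The 80% at 59 per group is inconsistent with the two-sided label and with the two-tailed 95% interval. On the plan's 5% vs 5% and 10% margin, the formula needs 75. At the 53-57 passers expected from 77 per arm, exact power is about 69-71% (Wald) or 51-55% (score). This rests only on the plan's own figures.
2. **A gap that should be closed.** The primary interval is unnamed. Wald and score give opposite verdicts in about 16% of trials at 59 per arm and 14-19% at 53-57, assuming a true 5% in both arms. The surgery-type tests cannot serve as confirmatory tests under a score interval. The documents give no sign that anyone intends to choose the method after seeing counts; the plan simply does not prevent it.
3. **Optional, secondary outcomes only.** The AUASS and UDI-6 models are valid. Using baseline more fully would multiply the week-6 contrast variance by 0.65-0.85 at assumed correlations of 0.3-0.7.

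**What to change.** **Sample Size Considerations.** State the alpha that matches the analysis (one-sided 0.025, equivalent to the two-tailed 95% interval), correct the table to 139/101/75/56/42, and replace the 80% claim with the exact power at 53-57 passers per arm under the interval to be used.

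**Statistical Methods, primary objective.** Before any counts are seen, name a score-type 95% interval (Miettinen-Nurminen or Newcombe) for the overall difference. Describe the surgery-type comparisons as estimates with intervals, without a non-inferiority verdict.

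**AUASS and UDI-6 (optional).** Constrain baseline means to be equal across arms, which keeps women without a baseline score, or use baseline as a covariate. Report the week-6 difference with its 95% interval. Adding site and surgery type is harmless but gains little.

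**Cost.** Wording only, with no new data; the downside is a visibly lower power. Restoring 80% takes more women. At 75 passers per arm exact power is 82% (Wald) or 69% (score), and the score interval reaches 80% at 95. At 30% failure these are 75/0.7 = 108 and 95/0.7 = 136 evaluable per arm, or 216 and 272 in total. Section 5 gives about 200 such operations in 12 months, so neither fits the one-year plan. If the sample cannot grow, the plan should state the lower power.
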